1.0 Objectives

1.1 Study Objectives

Describe the purpose, specific aims or objectives. State the hypotheses to be tested.

The purpose of the proposed study is to examine how replacement of habitually consumed snack foods in the U.S. with 2 oz./day of pecans affects markers of peripheral vascular health, lipids and lipoproteins, blood pressure, and glycemic control compared to usual U.S. intake.

The aims of the study are as follows:

- 1) To evaluate whether consuming 2 oz/day of pecans as a snack improves flow mediated dilation compared with habitual intake in individuals at elevated risk for cardiovascular disease;
- 2) To assess changes in pulse wave velocity, lipids and lipoproteins (concentration, particle size and number), blood pressure (central and peripheral) and glycemic control in each group.

Hypothesis:

It is hypothesized that replacement of typical snack foods with 2 oz./day of pecans will improve peripheral vascular assessments, lipid and lipoprotein profile and glycemic control compared to habitual average American intake.

1.2 Primary Study Endpoints

State the primary endpoints to be measured in the study.

Clinical trials typically have a primary objective or endpoint. Additional objectives and endpoints are secondary. The endpoints (or outcomes), determined for each study subject, are the quantitative measurements required by the objectives. Measuring the selected endpoints is the goal of a trial (examples: response rate and survival).

Flow Mediated Dilation (FMD)

1.3 Secondary Study Endpoints

State the secondary endpoints to be measured in the study.

Lipids and Lipoproteins (total cholesterol, LDL-cholesterol, HDL-cholesterol, triglycerides)
Lipoprotein particle size and number (LDL-cholesterol, HDL-cholesterol, VLDL and chylomicrons)
Pulse Wave Velocity (PWV)
Peripheral and Central Blood Pressure
Insulin, HbA1c and Fasting Glucose
Dietary intake of macronutrients, nutrients, and food groups
Diet Quality
Gut Microbiota composition

2.0 Background

2.1 Scientific Background and Gaps

Describe the scientific background and gaps in current knowledge.

For clinical research studies being conducted at Penn State Health/Penn State College of Medicine, and for other non-PSH locations as applicable, describe the treatment/procedure that is considered standard

of care (i.e., indicate how patients would be treated in non-investigational setting); and if applicable, indicate if the study procedure is available to patient without taking part in the study.

Current Dietary Guidelines for general health and prevention of chronic disease recommend a healthy dietary pattern U.S. Department of Health and Human Services (2016). In the U.S., habitual dietary patterns do not align with recommended health dietary patterns. Further, diet quality is suboptimal and thus strategies are needed to improve overall diet quality. The proposed trial aims to examine the cardiometabolic effects of pecans, when replacing a habitual snack. This trial will test the hypothesis that dietary incorporation of pecans to replace typical U.S. snack foods will improve diet quality and confer cardiometabolic benefits.

Pecans have the highest polyphenol content of any nut containing 1816 mg/100g (Ros, 2015). A significant proportion of the polyphenol content is flavanols (494 mg/100g), which are present in higher quantities than dark chocolate (246 mg/100g), blueberries (332 mg/100g) and red wine (313 mg/100g) (Gu et al., 2004). A meta-analysis of 11 studies showed that flow mediated dilation (FMD), a measure of endothelial function, increased by 1.34% after 2-18 weeks of consuming chocolate/cocoa/flavanols (Hooper et al., 2012). This change in FMD is clinically significant; for every 1% increase in FMD, the risk of CVD is reduced by 12% (Matsuzawa, Kwon, Lennon, Lerman, & Lerman, 2015). Furthermore, Balzer et al. showed flavanol rich cocoa containing 371 mg or 963 mg of flavanols improved FMD for 2 to 3 hours after consumption; consumption of 963 mg of cocoa flavonols for 30 days increased FMD by ~30% (Balzer et al., 2008). In the proposed study, the subjects will consume approximately 212 mg of flavanols (781 mg total polyphenols) from pecans as part of the healthy dietary pattern. Therefore, based on previous studies of phenolic rich foods, we hypothesize that the polyphenols in pecans will act on the vasculature to improve endothelial function.

Nuts, including walnuts, almonds, hazelnuts, pistachios and peanuts, improve endothelial function (Casas-Agustench, Lopez-Uriarte, Ros, Bullo, & Salas-Salvado, 2011; Neale, Tapsell, Guan, & Batterham, 2017), lipids and lipoproteins (Del Gobbo, Falk, Feldman, Lewis, & Mozaffarian, 2015), and glycemic control (Tindall, Johnston, Kris-Etherton, & Petersen, 2019; Vigiliouk et al., 2014). Previous studies have not investigated the effect of pecans on endothelial function. Three studies have shown that pecans tended to reduce total and LDL-cholesterol when consumed for 4 or 8 weeks, compared to a control diet without nuts (McKay, Eliasziw, Chen, & Blumberg, 2018; Morgan & Clayshulte, 2000; Rajaram, Burke, Connell, Myint, & Sabaté, 2001), which would be expected to improve vascular health. Furthermore, Hudthagosol et al. showed that 90 g of whole pecans or 90 g of blended pecans increased postprandial plasma levels of phenolic acid and flavanols, increased antioxidant capacity and decreased LDL-cholesterol oxidation, compared to an isocaloric macronutrient matched meal (Hudthagosol et al., 2011). In this study, vascular health was not measured. However, based on the increase in total plasma phenolic acid and flavanols is it likely that endothelial function would have been greater (improved) after consumption of the pecan-containing meals compared with the control meal.

Previous work from our lab has shown that foods rich in phenolic compounds exert health effects beyond those expected based on the macronutrient profile. For example, in a randomized, crossover controlled feeding study, a moderate fat diet (34% fat, 6% SFA, 17% MUFA, 9% PUFA, 49% CHO, 16% PRO) containing one-avocado per day lowered atherogenic lipids and lipoproteins more than a matched moderate fat diet without avocado (Wang, Bordi, Fleming, Hill, & Kris-Etherton, 2015). Specifically, the moderate fat diet containing one-avocado per day lowered LDL-cholesterol and non-HDL cholesterol (~13.5 mg/dL, ~14.6 mg/dL), relative to baseline and to a greater extent ($P<0.05$) than the matched moderate fat diet devoid of avocado (~8.3 mg/dL, ~8.7 mg/dL) and a low fat (LF; ~7.4 mg/dL, ~4.8 mg/dL) control diet. The greater improvements in lipids and lipoproteins with the moderate-fat diet containing avocado vs. the matched moderate-fat diet without avocado suggests beneficial effects beyond the fatty acid profile of the avocado; it is hypothesized that the bioactive compounds and the fiber content of avocados may explain the results of this previous study.

Similarly, in a randomized, crossover controlled feeding study comparing a heart healthy diet with walnuts to a fatty acid matched diet devoid of walnuts, and a diet lower in alpha-linoleic acid (ALA) and proportionately higher in oleic acid, we observed greater total cholesterol and LDL-cholesterol lowering (*unpublished*) and a greater reduction in aortic diastolic blood pressure (A. M. Tindall et al., 2019) with the walnut containing heart healthy diet vs. the low ALA diet; no difference was detected between the walnut containing diet and the fatty acid matched diet devoid of walnuts, and the fatty acid matched diet devoid of walnuts and the low ALA diet. This suggests that the fatty acid component of walnuts may not explain the full effect that we observed.

Based on these studies, we hypothesize that greater improvements in risk factors for cardiometabolic disease will be observed with incorporation of pecan into and average American diets vs. the typical U.S. diet. This research aligns with the current focus on food-based recommendations, by authoritative organizations, because of the inherent limitations associated with nutrient-focused recommendations. Furthermore, evidence generated may be used to support food-based recommendations for pecans, and since 2 oz/day (14 oz-eq/week) of pecans will be provided, the findings may be used to support higher intake recommendations for nuts, specifically pecans. The 2020-2025 Dietary Guidelines for Americans recommends (5 oz.-eq/week of nuts, seeds and soy at 2000 kcal).

2.2 Previous Data

Describe any relevant preliminary data.

Previous work from our lab has shown that foods rich in phenolic compounds exert health effects beyond those expected based on the macronutrient profile (Wang et al., 2015). In another randomized, crossover controlled feeding study comparing a heart healthy diet with walnuts to a fatty acid matched diet devoid of walnuts, and a diet lower in alpha-linoleic acid (ALA) and proportionately higher in oleic acid, we observed greater total cholesterol and LDL-cholesterol lowering and a greater reduction in aortic diastolic blood pressure (A. M. Tindall et al., 2019) with the walnut containing heart healthy diet vs. the low ALA diet; no difference was detected between the walnut containing diet and the fatty acid matched diet devoid of walnuts, and the fatty acid matched diet devoid of walnuts and the low ALA diet. This suggests that the fatty acid component of walnuts may not explain the full effect that we observed.

A significant proportion of the polyphenol content is flavanols (494 mg/100g), which are present in pecans in higher quantities than dark chocolate (246 mg/100g), blueberries (332 mg/100g) and red wine (313 mg/100g) (Gu et al., 2004). A meta-analysis of 11 studies showed that flow mediated dilation (FMD), a measure of endothelial function, increased by 1.34% after 2-18 weeks of consuming chocolate/cocoa/flavanols (Hooper et al., 2012).

Based on these studies, we hypothesize that greater improvements in risk factors for cardiometabolic disease will be detected following consumption of the average American diet with pecans versus typical US dietary intake.

2.3 Study Rationale

Provide the scientific rationale for the research.

A study with this design would provide the first empirical evidence to directly support the inclusion of pecans in a recommended healthy dietary pattern. In addition to providing evidence about the cardiometabolic effects of using pecans to improve the diet quality of an average American diet, this study will provide a feasible food-based approach that may be used to lower CVD risk.

Approximately, 50% of Americans are at risk for CVD (29) and therefore, the findings from this study will be of direct relevance to many Americans. Specifically, the results will be of interest to individuals who are managing their elevated CVD risk with lifestyle strategies and pharmacotherapy; this study will test another lifestyle strategy that can be implemented to lower CVD risk.

The findings of this trial utilizing a non-pharmaceutical approach will be applicable to overweight and obese adults living with one or more symptoms of metabolic syndrome and are therefore at increased risk of cardiovascular disease in the US, and thus will be of substantial public interest.

3.0 Inclusion and Exclusion Criteria

Create a numbered list below in sections 3.1 and 3.2 of criteria subjects must meet to be eligible for study enrollment (e.g., age, gender, diagnosis, etc.).

Vulnerable Populations:

Indicate specifically whether you will include any of the following vulnerable populations in this research. You MAY NOT include members of these populations as subjects in your research unless you indicate this in your inclusion criteria because specific regulations apply to studies that involve vulnerable populations.

The checklists referenced below outline the determinations to be made by the IRB when reviewing research involving these populations. Review the checklists as these will help to inform your responses throughout the remainder of the protocol.

- **Children** –Review “HRP-416- Checklist - Children”
- **Pregnant Women** – Review “HRP-412- Checklist - Pregnant Women”
- **Cognitively Impaired Adults**- Review “HRP-417- Checklist - Cognitively Impaired Adults”
- **Prisoners**- Review “HRP-415- Checklist - Prisoners”
- **Neonates of uncertain viability or non-viable neonates**- Review “HRP-413- Checklist - Non-Viable Neonates” or “HRP-414- Checklist - Neonates of Uncertain Viability”

[Do not type here]

3.1 Inclusion Criteria

Create a numbered list of the inclusion criteria that define who will be included in your final study sample (e.g., age, gender, condition, etc.)

- 1) 25-70 years of age
- 2) BMI 25-40 kg/m²
- 3) ≥ 1 criterion for metabolic syndrome (i.e., waist circumference ≥ 94 cm men or ≥ 80 cm women; triglycerides ≥150 mg/dL; HDL-cholesterol ≤ 40 mg/dL men or ≤ 50 mg/dL women; systolic blood pressure ≥130 mmHg or diastolic blood pressure ≥85 mmHg; fasting plasma glucose ≥100 mg/dL) at screening.

3.2 Exclusion Criteria

Create a numbered list of the exclusion criteria that define who will be excluded in your study.

- 1) Current use of tobacco-containing products or (≤6 months) cessation
- 2) Allergy/sensitivity/intolerance/dislike of study foods
- 3) Women who are pregnant, lactating, planning to become pregnant or have given birth in the past year

- 4) Individuals who have had a cardiovascular event (heart attack, revascularization, stroke), or have a history of heart failure, liver, kidney, autoimmune diseases or inflammatory conditions such as gastrointestinal disorders or rheumatoid arthritis.
- 5) Type 1 or type 2 diabetes
- 6) Unstable weight $\geq 10\%$ body weight for 6 months prior to enrollment
- 7) Systolic blood pressure >160 mmHg and/or diastolic blood pressure >100 mmHg at screening
- 8) Fasting blood glucose ≥ 126 mg/dL at screening
- 9) Triglycerides ≥ 350 mg/dL at screening
- 10) Taking any medications known to affect lipids, blood pressure, or blood glucose levels
- 11) Diagnosed inflammatory conditions or taking prescribed anti-inflammatory medications
- 12) Use of antibiotics within the prior 8 weeks
- 13) Taking supplements (e.g., psyllium, fish oil, soy lecithin, and phytoestrogens) and botanicals known to affect study outcomes and not willing to cease for the duration of the study
- 14) Individuals consuming >14 alcoholic drinks/week, and not willing to avoid alcohol consumption for 48 hours prior to test visit
- 15) Pre-menopausal women who do not have a regular menstrual cycle of 25-35 days
- 16) PI discretion

3.3 Early Withdrawal of Subjects

3.3.1 Criteria for removal from study

Insert subject withdrawal criteria (e.g., safety reasons, failure of subject to adhere to protocol requirements, subject consent withdrawal, disease progression, etc.).

Failure to comply with study procedures.

Participant withdraws consent.

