3.3.2 Follow-up for withdrawn subjects

Describe when and how to withdraw subjects from the study; the type and timing of the data to be collected for withdrawal of subjects; whether and how subjects are to be replaced; the follow-up for subjects withdrawn from investigational treatment.

No safety concerns; no reason for follow-up. If consent is withdrawn no data from the participant will be used. Otherwise, if consent is not withdrawn, data from individuals who withdraw from the study may be used in an intent-to-treat analysis but another individual will be enrolled for each participant who drops out to ensure that an adequate sample size (with complete data) is reached.

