7.1 Study Design

Describe and explain the study design.

A two-arm randomized parallel study is proposed. Subjects will be randomized to one of the following attention and resource matched conditions for approximately 12-weeks: 1) education to consume 2 oz./day of pecans in place of the snacks they usually eat (AAD+P); 2) continue consuming their current diet (AAD) with provision gift cards worth \$30 monthly (equivalent value to the pecans) and matched contact with study personnel.

Assessment of outcomes will occur at baseline and the end of the treatment period (week 12). Pre-menopausal women will be scheduled for testing within 7 days of starting their menstrual period to control for hormonal effects on vascular function. Therefore, the treatment periods may be adjusted as needed. At the baseline and 12-weeks two blood samples will be collected (separated by at least 24-hours) for endpoint analysis. Weight will be measured on both days at each timepoint. Flow mediated dilation, central and peripheral blood pressure and pulse wave velocity will be measured on one day at each time point. Diet intake will be assessed at baseline, week 6, and week 12 using 24-hour recalls. Subjects will also provide a fecal collection at baseline and 12 weeks.

7.2

Study Procedures

Provide a step by step description of all research procedures being conducted (broken down by visit, if applicable) including such information as below (where and when applicable); describe the following:

- HOW: (e.g., data collection via interviews, focus groups, forms such as surveys and questionnaires, medical/school records, audio/video/digital recordings, photographs, EKG procedures, MRI, mobile devices such as electronic tablets/cell phones, observations, collection of specimens, experimental drug/device testing, manipulation of behavior/use of deception, computer games, etc.)
- WHERE: (e.g., classrooms, labs, internet/online, places of business, medical settings, public spaces, etc.)

[Type protocol text here]

7.2.1 Visit 1 or Day 1 or Pre-test, etc.

Provide a description of what procedures will be performed on visit 1 or day 1 or pre-test in order of how these will be done. If your study only involves one session or visit, use this section only and indicate 7.2.2 as not applicable.

Participants will be consented prior to any screening activities.

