8.0 Number of Subjects and Statistical Plan

8.1 Number of Subjects

Indicate the maximum number of subjects to be accrued/enrolled. Distinguish between the number of subjects who are expected to be enrolled and screened, and the number of subjects needed to complete the research procedures if applicable (i.e., numbers of subjects excluding screen failures.)

A sample size of 128 (64 per group) is needed. To complete 128 individuals, approximately 140 participants will be recruited to account for an anticipated ~10% dropout rate.

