8.3 Statistical methods

Describe the statistical methods (or non-statistical methods of analysis) that will be employed.

The normality of the data will be tested before performing analyses, and transformations will be made if needed. In the primary analyses, the change in outcome measures (baseline to 12 weeks) will be compared between groups after adjustment for baseline value, age, sex, and BMI. The mixed model

procedure will be used (SAS) with randomization as a fixed factor, and baseline value for the outcome measure, age, sex, and BMI included as covariates.

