13.0 Subject Payment and/or Travel Reimbursements

Describe the amount, type (cash, check, gift card, other) and timing of any subject payment or travel reimbursement. If there is **no** subject payment or travel reimbursement, indicate as not applicable.

Extra or Course Credit: Describe the amount of credit **and** the available alternatives. Alternatives should be equal in time and effort to the amount of course or extra credit offered. It is not acceptable to indicate that the amount of credit is to be determined or at the discretion of the instructor of the course.

Approved Subject Pool: Indicate which approved subject pool will be used; include in response below that course credit will be given and alternatives will be offered as per the approved subject pool procedures.

For their time and participation in the study participants will receive monetary compensation of up to \$200 (check or direct deposit). For participants who withdraw from the study, compensation will be prorated as follows and paid at the completion of their participation in the study:

Completion of day 1 and day 2 testing at baseline = \$50
Completion of three 24-hour recalls at baseline= \$25
Completion of three 24-hour recalls at week 6 = \$25
Completion of day 1 and day 2 testing at 12 weeks = \$75
Completion of three 24-hour recalls at week 12 = \$25

Payments will be made at the completion of a participant's involvement with the study.

Participants may not be eligible for compensation if determined that specific work or visa laws conflict.

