Cardiometabolic Effects of Pecans as a Snack

NCT05071807

September 19, 2023

The sample size calculation was based on FMD, the primary outcome. To detect a 1.2 percentage point (standard deviation 2.4; effect size 0.5) between-group difference in the change in FMD with 80% power ($\alpha=0.05$), it was estimated that a sample size of 128 participants was needed (64 per group) (40-43).

All analyses were performed in SAS (version 9.4; SAS Institute Inc.). All data collected from randomly assigned participants were included in data analyses consistent with intent-to-treat principles. All residuals for regression models were checked for normality via normal probability (Q-Q) plots. When the residuals were non-normally distributed, log transformation was conducted, which improved the residual distribution to approximately normal. Linearity was investigated by plotting model residuals against the outcome of interest and for all variables the assumption of linearity was met. All models were adjusted for outcome baseline value, age (years), sex (male or female) and baseline BMI (kg/m²). For all described tests, effect modification by sex was examined by evaluating the group by sex interaction. If the group by sex interaction main effect was not significant it was excluded from the final model. The primary analyses for the vascular and cardiometabolic outcomes assessed between group (pecan or usual diet) differences in the change from baseline. The change from baseline was calculated by subtracting the endpoint value from the baseline value. Weight, lipids/lipoproteins, glucose and insulin were measured on two test days at each time point and values were averaged for analysis to improve measurement precision. Between-group differences in the change from baseline for all vascular and cardiometabolic outcomes were assessed using linear regression models.

For diet quality, linear mixed models were used to account for the repeated nature of the outcome. Group was included as a fixed effect and time point was included as a repeated effect. Intervention effects were determined by examining the group by visit interaction. When a significant group by time point interaction was detected, post hoc testing was conducted and the Tukey-Kramer method was used to adjust for multiple comparisons. Statistical significance was set at $p < 0.05$.

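### Participants removed for non-compliance have no planned week-12 FMD, so the analysis called intent-to-treat covers only those who reach week 12

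*Protocol*

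**What the plan says.** Protocol section 3.3.1 gives two grounds for removal from the study: withdrawal of consent, and "Failure to comply with study procedures". No threshold or definition is attached to the second.

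The template prompt in section 3.3.2 asks what data will be collected from withdrawn participants, and when. The answer begins "No safety concerns; no reason for follow-up. If consent is withdrawn no data from the participant will be used". It then allows data from those who leave without withdrawing consent to be used in an intent-to-treat analysis, and adds that "another individual will be enrolled for each participant who drops out to ensure that an adequate sample size (with complete data) is reached".

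Sections 7.1 and 7.2.3 place FMD at baseline and at the end of the 12-week period, with nothing in between. Section 8.1 states that "approximately 140 participants will be recruited to account for an anticipated ~10% dropout rate", the target being 128 completers.

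For the analysis, protocol section 8.3 says "the change in outcome measures (baseline to 12 weeks) will be compared between groups after adjustment for baseline value, age, sex, and BMI". The SAP fits linear regression models to the change from baseline and states: "All data collected from randomly assigned participants were included in data analyses consistent with intent-to-treat principles". It names no imputation, no missing-data assumption and no sensitivity analysis.

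**The concern.** Removal for non-compliance happens after randomisation and can depend on the assigned arm. One arm is asked to change its daily diet; the other carries on as usual. Section 10.0 also lists gastrointestinal upset as a possible effect of adding pecans. If removal is more frequent in one arm, and those removed would have had different FMD changes, the comparison is no longer between the groups as randomised.

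Replacing each dropout does not itself cause bias. It restores the number of completers but does not recover the lost outcomes. A reader of the SAP would also take the analysed set to be the randomised set, which it cannot be for FMD.

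A smaller inconsistency sits beside this. Section 3.3.2 discards all data from anyone who withdraws consent, while the SAP says that all data collected from randomised participants were included.

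**Working it through.** **1. Can a removed participant enter the FMD analysis?**

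- FMD exists at baseline and week 12 only (Protocol 7.1, 7.2.3).
- No section asks for a week-12 visit after removal (Protocol 3.3.1, 3.3.2).
- The outcome is a single change score (Protocol 8.3; SAP). The mixed model named in section 8.3 does not help, because baseline is a covariate and each person contributes one value. Without week-12 FMD there is nothing to model.

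So the answer is no. Someone who eats few pecans but attends week 12 is still analysed as randomised; the problem is confined to those removed. Diet quality is less exposed, because it also has a week-6 measurement.

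**2. The plan's own figures**

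- Inputs: difference 1.2 percentage points, SD 2.4, alpha 0.05 (taken as two-sided), 64 per group (Protocol 8.2; SAP).
- The two-sample t-test with 64 per group has power 80.1%, so the stated 128 reproduces. The normal approximation used below gives 80.7%.
- SE = 2.4 × √(2/64) = 0.424.
- Expected loss for any reason: 140 − 128 = 12 (12/140 = 8.6%), or 10% of 140 = 14. The share due to non-compliance is not given.

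**3. Size of the possible bias (assumptions, not document figures)**

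Let shares pP (pecan) and pC (control) be removed, and let those removed have an FMD change k points lower than those retained, after covariate adjustment. Then

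bias = k × (pP − pC).

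With k = 1.2 or 2.4 (0.5 or 1 SD): 1.2 × 0.08 = 0.096 and 2.4 × 0.08 = 0.192.

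| Removed, pecan / control | k | Bias (points) | Two-sided type I error | Power at a true 1.2 |
|---|---|---|---|---|
| equal | any | 0 | 5.0% | 80.7% |
| 10% / 2% | 1.2 | +0.096 | 5.6% | 86.3% |
| 10% / 2% | 2.4 | +0.192 | 7.4% | 90.7% |
| 2% / 10% | 1.2 | −0.096 | 5.6% | 74.0% |
| 2% / 10% | 2.4 | −0.192 | 7.4% | 66.1% |

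The higher power in the second and third rows is a product of the bias, not a gain. As a share of the planned difference, 0.096/1.2 = 8% and 0.192/1.2 = 16%.

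**4. A simpler scenario as a cross-check**

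Suppose 10% of the pecan arm only is removed, and these people would have had no pecan effect. The difference over everyone randomised is 1.2 × 0.90 = 1.08 points, while the analysis of those retained targets 1.20. The gap is 0.12 points, or 10% of the planned difference, which lies inside the range above.

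**The case against.** The strongest reply is that selection on compliance is possible but not shown. Section 3.3.1 speaks of study procedures, not pecan intake. It may mean missed visits or forms, and people who stop attending would lack week-12 FMD under any rule. The phrase about follow-up in section 3.3.2 can be read as safety follow-up only. This stands as a limit on the claim. It does not close the gap: on either reading, no outcome-collection plan exists for those removed, and permission to use their data is of no use for FMD when no week-12 value has been collected.

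The scenarios are also fair game. Removing 10% of one group of 70 and 2% of the other is 7 + 1.4 = 8.4 people, or 60% to 70% of the 12 to 14 losses expected for all reasons, with a five-to-one imbalance that no section supports. The type I error figures suppose no pecan effect, so the gap k would have to be purely prognostic. The power loss supposes removed controls who do worse, although they have no pecan benefit to lose. If missingness depends only on arm, baseline FMD, age, sex and BMI, and the model is correct, the planned regression is unbiased without any repair. All of this stands, and it is why the figures are illustrations.

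Finally, multiple imputation from those same variables returns essentially the planned estimate under missing at random. That is right: only the analysis of departures from that assumption adds information.

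**Conclusion.** The point holds. The documents permit removal for non-compliance, plan no week-12 FMD for those removed, and analyse one change score per person with no missing-data method. The primary analysis is therefore of randomised participants with week-12 FMD, and describing it as intent-to-treat without qualification overstates what it covers.

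The likely effect is modest: about 0.10 to 0.19 points either way under the assumed 10% against 2% removal and gaps of 1.2 to 2.4 points, and zero with equal removal and equal gaps. The actual size and sign cannot be found, because the documents give no removals by arm or reason. This merits correction because it concerns the primary endpoint and is cheap to repair; it does not show that the trial's result is wrong.

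**What to change.** **Protocol 3.3.1 and 3.3.2.** Separate stopping the intervention from stopping outcome collection. State that every randomised participant who has not withdrawn consent is invited to the week-12 visits whatever their adherence, and is analysed in the assigned group. No change to when the intervention stops is proposed.

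**SAP.**

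1. Name the primary analysis set as randomised participants with week-12 FMD.
2. Report numbers randomised, removed (with reason) and analysed, by arm.
3. Add one missing-data sensitivity analysis, for example multiple imputation using arm, baseline FMD, age, sex and BMI. Shift the imputed FMD changes up and down in each arm separately; shifts of 1.2 and 2.4 points would match the illustration above.
4. State how data from people who withdraw consent are handled, so that the SAP agrees with section 3.3.2.

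**Cost.** Section 13.0 pays $75 for "Completion of day 1 and day 2 testing at 12 weeks". If all 14 anticipated dropouts attended, that is 14 × $75 = $1,050, plus staff and assay time; fewer would attend in practice, since those who withdraw consent would not. The estimate may also shrink. If 8.6% to 10% of the pecan arm were non-compliant with no effect, the difference over all 70 per arm would be 1.10 to 1.08 points, with t-test power 77% to 75%.

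The SAP is written in the past tense, which suggests that data collection is over. In that case the extra visits are no longer possible and cost nothing, but the four SAP items still apply.
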